2.2 Analysis set

The **all treated subjects (ATS)** analysis set includes all patients who receive at least one dose of eltrombopag.

2.3 Patient disposition, demographics and other baseline characteristics

The ATS will be used for disposition, demographic and other baseline summaries and listings.

2.3.1 Patient disposition

Disposition data will be summarized descriptively.

2.3.2 Patient demographics and other baseline characteristics

Demographic and other baseline data will be summarized descriptively.

Medical histories and current medical conditions at baseline will be listed.

2.4 Treatments (study treatment, rescue medication, concomitant therapies, compliance)

2.4.1 Study treatment

Duration of eltrombopag exposure (months) will be summarized descriptively and listed for the ATS.

Duration of eltrombopag exposure (months) will also be categorized and summarized using the following time intervals: $<1, \ge 1, \ge 3, \ge 6, \ge 12, \ge 24, \ge 36, \ge 48, \ge 60$.

A listing will also be provided of study treatment compliance (tablets/sachets dispensed and returned).

2.4.2 Concomitant medications

Concomitant medications will be listed.

2.5 Analysis of the primary objective

2.5.1 **Primary endpoint**

The analyses of the primary endpoint (AEs) are described in Section 2.6.

2.6 Safety analyses

The ATS will be used for safety summaries and listings.

2.6.1 Adverse events (AEs)

The AEs will be re-coded using the latest version of the medical dictionary for regulatory activities (MedDRA) at the time of the analysis.

AEs will be graded using the common toxicity criteria for adverse events (CTCAE) Version 4.03. If a patient reported more than one AE with the same preferred term (PT), the AE with the greatest severity will be presented. If a patient reported more than one AE within the same primary system organ class (SOC), the patient will be counted only once with the greatest severity at the SOC level, where applicable. An AE with missing CTCAE grade will be included in the 'All grades' column of the summary tables.

In AE summaries, the primary SOC will be presented alphabetically and the PTs will be sorted within the primary SOC in descending frequency.

Summary tables will be provided for:

- All AEs regardless of relationship to study treatment by primary system organ class (SOC), preferred term (PT) and maximum severity
 - In-text table by SOC and maximum severity
 - In-text table by PT and maximum severity
- AEs suspected to be related to study treatment by SOC, PT and maximum severity
 - In-text table by PT and maximum severity
- AEs leading to treatment discontinuation regardless of relationship to study treatment by SOC, PT and maximum severity
 - In-text table by PT and maximum severity
- Serious AEs (SAEs) regardless of relationship to study treatment by SOC, PT and maximum severity
 - In-text table by PT and maximum severity
- On-treatment deaths by SOC and PT
 - In-text table by PT
- All deaths by SOC and PT
- *Non-SAEs regardless of relationship to study treatment (threshold=0%) by SOC and PT
- *On treatment deaths and SAEs by SOC and PT

*For the legal requirements of EudraCT, two required tables on <on-treatment/treatment emergent> AEs which are not SAEs with an incidence greater than x% and on <on-treatment/treatment emergent> SAEs and SAE suspected to be related to study treatment will be provided by SOC and PT on the ATS.

If for a same patient, several consecutive AEs (irrespective of study treatment causality, seriousness and severity) occurred with the same SOC and PT:

- a single occurrence will be counted if there is ≤ 1 day gap between the end date of the preceding AE and the start date of the consecutive AE
- more than one occurrence will be counted if there is > 1 day gap between the end date of the preceding AE and the start date of the consecutive AE

For occurrence, the presence of at least one SAE/SAE suspected to be related to study treatment/non SAE has to be checked in a block e.g., among AEs in $a \le 1$ day gap block, if at least one SAE is occurring, then one occurrence is calculated for that SAE.

Novartis	For business use only	Page 11
SAP and TFLs		CETB115BRU01/Eltrombopag

The number of deaths resulting from SAEs suspected to be related to study treatment and SAEs irrespective of study treatment relationship will be provided by SOC and PT.

A listing will be provided for all AEs. Records outside of on-treatment period will be flagged.

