MedDRA	medical dictionary for drug regulatory affairs
PDS	programming data specifications
PT	preferred term
SAE	serious adverse event
SAP	statistical analysis plan
sd	standard deviation
SOC	system organ class

1 Introduction

This statistical analysis plan (SAP) provides detailed statistical methodology for the analyses of data which will be used for preparation of the ETB115BRU01 (TRA117366) clinical study report (CSR) and is based on the study protocol amendment 01, dated 08-Jul-2013.

The output shells information is in Section 7, the in-text table shells are in Section 8, the posttext tables and listings are in Section 9 and Section 10 respectively. Programming specifications for datasets, including derivation of variables, are given in the programming data specifications (PDS) document.

All data will be analyzed by and then imported to the Novartis global programming & statistical (GPS) environment. Analysis data sets and statistical outputs will be produced using the SAS system Version 9.3 or higher.

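### The EudraCT occurrence rule measures the gap only from the preceding record, so one continuing event can count as two or more when shorter same-term records lie inside it

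*SAP*

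**What the plan says.** SAP 2.6.1 introduces the rule with "For the legal requirements of EudraCT, two required tables on" non-serious AEs and on SAEs, including SAEs suspected to be related to treatment. It applies where, in one patient, "several consecutive AEs (irrespective of study treatment causality, seriousness and severity) occurred with the same SOC and PT". Two branches follow:

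- Merge: "a single occurrence will be counted if there is ≤ 1 day gap between the end date of the preceding AE" and the start of the next one.
- Split: "more than one occurrence will be counted if there is > 1 day gap between the end date of the preceding AE and the start" of the next one.

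The SAP then says how a block is counted when it contains a serious event: "day gap block, if at least one SAE is occurring, then one occurrence is calculated for that SAE".

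Section 2.6.1 gives no sort order and does not mention overlapping or nested records. It also does not say whether a gap is a difference between dates or a number of clear days.

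**The concern.** The rule is meant to separate a term that stopped and came back from one that carried on. The end of the immediately preceding record is a safe marker for this only when records follow each other without overlap. If a long record is followed by a short one inside it, the short record's end date becomes the reference and the long record is forgotten. The next record is then judged against a date long past, although the event is still documented as ongoing.

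At stake is the accuracy of two tables that the SAP describes as legally required. The study enrols at most 12 patients (Protocol section 3; SAP 1.1), so event counts will be small and one spurious occurrence would be visible.

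**Working it through.** The plan gives no figure to reproduce, so the check applies the written rule to short illustrative record sets.

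**Inputs**

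- Records pooled: same patient, SOC and PT, whatever their seriousness (SAP 2.6.1).
- Threshold: 1 day (SAP 2.6.1).
- Reference date: end of the preceding record (SAP 2.6.1).
- Example dates: assumed, all complete, so no date imputation is involved.

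**Formulas**, with records sorted by start date, S for start and E for end:

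- SAP rule: gap g = S(i) − E(i−1). A new occurrence starts if g > 1.
- Running-end rule: gap h = S(i) − the latest E among all earlier records in the block. A new occurrence starts if h > 1.

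**Main example: days 1-100, 10-12, 50-52**

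- Second record: g = 10 − 100 = −90 and h = −90. Both rules keep it in the first block.
- Third record: g = 50 − 12 = 38, so the SAP rule starts a new block. h = 50 − 100 = −50, so the running-end rule does not.
- Count: 2 under the SAP rule, 1 under the running-end rule. The first record covers every day from 1 to 100, so there is no event-free interval to justify the second occurrence.

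**Other cases**

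| Records (days) | Deciding gap, SAP rule | SAP count | Running-end count |
|---|---|---|---|
| 1-60, 10-12, 30-32 | 30 − 12 = 18 | 2 | 1 |
| 1-100, 10-12, 50-52, 80-81 | 50 − 12 = 38; 80 − 52 = 28 | 3 | 1 |
| 1-3, 4-6 (control) | 4 − 3 = 1 | 1 | 1 |
| 1-60, 10-12 (control) | 10 − 60 = −50 | 1 | 1 |

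The controls show that back-to-back records, and a long record with a single short one inside it, are counted correctly.

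**Sensitivity to what the SAP leaves open**

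- Gap as clear days: each gap falls by 1 (38 to 37, 28 to 27, 18 to 17). All stay above 1, so the counts do not change.
- Sort by end date: the main example becomes 10-12, 50-52, 1-100. The gaps are 50 − 12 = 38 (new block) and 1 − 52 = −51 (same block), so the count is still 2. The running-end rule also gives 2 in this order, so the correction must state the sort by start date.

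**Direction.** With records sorted by start date, the preceding end date can never be later than the latest end date so far. So g is never smaller than h, and the SAP rule can only match or exceed the running-end count.

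**Serious events.** If all three records in the main example are SAEs, each of the two blocks contains one, and the SAP rule gives 2 SAE occurrences instead of 1.

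**The case against.** The strongest defence is that the rule addresses consecutive AEs and was never meant for nested ones. The pattern needs at least three records of one term in one patient, with two separated records inside a longer one. Protocol section 8 provides for data cleaning, where overlapping records of the same term could be queried. SAP section 1 adds: "Programming specifications for datasets, including derivation of variables, are given in the programming data specifications (PDS) document". That document was not available and may define the reference date differently. All AEs are listed, and with at most 12 patients a split event can be found by eye. These points limit the importance of the problem, but they do not remove it. The SAP states the rule in operational terms, the literal result is wrong for this pattern, and nothing in the protocol or SAP corrects it.

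A reader might also infer that the rule undercounts serious events. With an SAE on days 10-12, a non-serious record on days 13-40 and an SAE on days 41-43, all three chain together and give one SAE occurrence, although the SAEs are 29 days apart (41 − 12). The documents do not support calling this an error. The SAP says openly that records are chained regardless of seriousness, and it deals directly with blocks of mixed seriousness. Its split branch compares neighbouring records only, so it contains no rule that any two SAEs more than 1 day apart must count separately. Forming separate blocks by seriousness would bring its own miscount. One continuous event recorded as non-serious on days 1-9, serious on days 10-12 and non-serious on days 13-60 would give 2 non-serious occurrences (13 − 9 = 4 days) where the SAP rule gives 1.

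**Conclusion.** The point holds in a small form. Read literally, the rule overcounts occurrences when separated records of one SOC and PT lie inside a longer record: 2 instead of 1 with two such records, 3 instead of 1 with three. This does not depend on the sort order or on the meaning of gap. It does rest on reading the reference to the preceding record as written, and on such record sets occurring.

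The documents do not show how often they occur, so no expected error can be given for the tables as a whole. A reader should not infer that many counts will be wrong.

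The effect is confined to occurrence counts in the two EudraCT tables. The patient-level n (%) tables, which carry the primary endpoint, are untouched. For several AEs within one SOC, for instance, "the patient will be counted only once with the greatest severity at the SOC level". This is a minor correction to a stated algorithm.

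**What to change.** Amend the occurrence rule in SAP 2.6.1 to say: sort each patient's records of the same SOC and PT by start date, and start a new occurrence only if a record's start date is more than 1 day after the latest end date among all earlier records in the block. The PDS should match. The chaining of records regardless of seriousness can stay as it is.

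The cost is one sentence and a small programming change, with no new data. Counts can only stay the same or fall. One consequence should be accepted knowingly. If the record on days 1-100 is non-serious and those on days 10-12 and 50-52 are SAEs, the SAE count goes from 2 (one SAE in each of two blocks) to 1 (both in one block). This follows from the SAP's own convention of one SAE occurrence per block.

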2.6.2 Deaths

See Section 2.6.1. A listing will be provided of all deaths, deaths outside of on-treatment period will be flagged.

2.6.3 Laboratory data

Laboratory values will be converted to the international system of units (SI). CTCAE Grade 0 will be assigned for all non-missing values not graded as 1 or higher. Grade 5 will not be used. For laboratory tests where grades are not defined by CTCAE version 4.03, results will be categorized as low/normal/high based on laboratory normal ranges.

The following summaries will be provided. Note that except for baseline value only ontreatment values will be used in summaries.

- Shift tables using CTCAE grades to compare baseline to the worst on-treatment value for platelets, hemoglobin and white blood cells (WBCs).
- Figure for median platelet counts over time (baseline and every 8 weeks post-baseline). Horizontal reference lines to be added at 30, 50 and 100 Gi/L. Interquartile range (IQR) to be added as vertical lines.

Listings of all laboratory data (hematology, biochemistry, urinalysis, coagulation, pregnancy test etc.) will be provided showing the corresponding CTCAE grades, if applicable, and the classifications relative to the laboratory normal ranges. Values measured outside of on-treatment period will be flagged.

Liver function parameters

Liver function parameters of interest are total bilirubin (TBL), alanine aminotransferase (ALT), aspartate aminotransferase (AST) and alkaline phosphatase (ALP).

The number (%) of patients with worst on-treatment values will be summarized. For single lab parameter lines (e.g. AST >3xULN) the worst value post-baseline is considered. For combination of various parameters (e.g. ALT or AST > 3xULN & TBL > 2xULN & ALP < 2xULN) the lab values need to be from the same assessment (concurrent measurements).

Listings of all liver event data will be provided. Values measured outside of on-treatment period will be flagged.

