## 5.8.1.2. Liver Chemistry Monitoring Criteria

For subjects with ALT  $\ge 3x$  ULN **but** < 5x ULN **and** bilirubin < 2x ULN, without hepatitis symptoms or rash, and who can be monitored weekly for 4 weeks, the following actions should be taken:

- Notify the GSK Medical Monitor within 24 hours of learning of the abnormality to discuss subject safety
- Can continue study treatment
- Must return weekly for repeat liver chemistries (ALT, AST, alkaline phosphatase, bilirubin) until they resolve, stabilize or return to within baseline values
- If at any time the subject meets any of the liver chemistry stopping criteria 1-5, proceed as described above
- If, after 4 weeks of monitoring, ALT <3x ULN and bilirubin <2x ULN, monitor subjects twice monthly until liver chemistries normalize or return to within baseline values.

Refer to Appendix 1 for algorithm of liver chemistry monitoring, stopping and follow up criteria.

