# 9. DATA ANALYSIS AND STATISTICAL CONSIDERATIONS

# 9.1. Hypotheses

Subjects are being assessed to investigate the safety of eltrombopag.

Since this is an open-label study there are no formal statistical hypothesis tests planned.

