# 9.3.5.1.3. Clinical Laboratory Evaluations

Hematology and clinical chemistry data will be displayed at each scheduled assessment according to NCI CTCAE grade. Unscheduled data will be included in "overall" and "any post-screening" displays which will capture a worst case across all scheduled and unscheduled visits post first dose of study medication.

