2.9 Interim analysis

Not applicable.

3 Sample size calculation

Approximately 12 patients were planned to be enrolled. As this is an extension study for pediatric chronic ITP patients the sample size was based on the number of patients previously enrolled in the TRA115450/PETIT2 study.

4 Change to protocol specified analyses

Data will be displayed according to Novartis (not GlaxoSmithKline(GSK)) reporting standards.

Primary endpoint clarified as the frequency of all AEs.

6 Appendix

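### SAP 2.6.3 plans no baseline-to-worst shift table for liver tests, so its summary tables cannot separate a carried-over liver elevation from a new or worsening one

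*SAP*

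**What the plan says.** SAP 2.6.3 (Laboratory data) plans two general laboratory summaries. One is a figure of median platelet count over time. The other is "Shift tables using CTCAE grades to compare baseline to the worst on-treatment value for platelets, hemoglobin and white blood cells (WBCs".

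Liver tests are handled in a separate paragraph: "Liver function parameters of interest are total bilirubin (TBL), alanine aminotransferase (ALT), aspartate aminotransferase (AST) and alkaline phosphatase (ALP". For these, "The number (%) of patients with worst on-treatment values will be summarized". For lines on a single parameter, "the worst value post-baseline is considered"; combination lines need values from the same assessment. No liver line is conditioned on, split by or shifted from baseline. All laboratory data, biochemistry included, are listed with CTCAE grade and normal-range class.

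Protocol 9.3.5.1.3 states: "Hematology and clinical chemistry data will be displayed at each scheduled assessment according to NCI CTCAE grade". It adds overall and post-screening displays of the worst value after the first dose. SAP Section 4 records two changes from the protocol, the reporting standards and the primary endpoint, and does not mention chemistry.

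**The concern.** Laboratory assessments are a named safety endpoint in both documents. Liver chemistry is also the only laboratory criterion listed for mandatory permanent discontinuation (Protocol 4.2.1 and 5.8.1). What a long-term extension should show about the liver is whether tests become abnormal, or get worse, during the study.

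The SAP uses a design that answers this for three haematology parameters and leaves it out for liver tests. A reader of the liver table alone could take an elevation brought in from the parent study for one that arose in this study.

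**Working it through.** **1. Which tests have a baseline comparison.** Collection is from Protocol Table 3 and its footnotes 6 and 8; summaries are from SAP 2.6.3.

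| Test | Drawn on Day 1 | Baseline-to-worst shift | Worst post-baseline count | Listed |
|---|---|---|---|---|
| Platelets, hemoglobin, WBC | yes | yes | no | yes |
| ALT, AST, ALP, total bilirubin | yes | no | yes | yes |
| Direct bilirubin | yes | no | not named | yes |

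The chemistry panel consists of these five liver analytes, so no scheduled chemistry test has a summary against baseline. The data for one are collected.

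**2. What the counting rule does.** SAP 2.1.1 starts the window for on-treatment assessments the day after the first dose, so the Day 1 value is not itself counted. For a given threshold line:

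- Above on Day 1, below at every later assessment: not counted.
- Above on Day 1, still above at one or more later assessments: counted.
- Below on Day 1, above later: counted.

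The second and third patients look the same in the table.

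**3. Whether the second patient can occur.**

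- Protocol 5.1.2 carries patients over on their parent-study dose unless an adjustment is warranted.
- Protocol 4.1.2 and 4.1.3 set no numeric liver limit for entry.
- Table 3 first schedules chemistry on Day 1, and the only baseline result that Protocol 7.1 names for review before treatment starts is the pregnancy test.
- During treatment, Protocol 5.8.1.2 says of a patient with ALT at least 3 and below 5 times ULN, bilirubin below 2 times ULN, no symptoms and weekly monitoring: "Can continue study treatment".

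So the situation is possible. The documents do not say how often it occurs.

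**4. Size.** There is no powered figure to reproduce. Protocol 9.1 says "Since this is an open-label study there are no formal statistical hypothesis tests planned", and SAP Section 3 says "Approximately 12 patients were planned to be enrolled", a number set by the parent study. The figures below are illustrations.

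- One patient of 12: 1/12 = 8.3% (exact 95% interval 0.2% to 38.5%).
- Assumed counts: two of 12 meet a liver line, and one of them already met it on Day 1. The table reports 2/12 = 16.7%. New elevations are 1/11 = 9.1% of patients not elevated at baseline, or 1/12 = 8.3% of all patients.
- Assumed prevalence p of elevation at entry, patients independent: the chance that at least one of 12 enters elevated is 1 − (1 − p)^12. For p = 2%, 5%, 10% and 20% this gives 22%, 46%, 72% and 93%. The chance that such an elevation is also counted is no larger, because it must still be present after Day 1.

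**The case against.** Several points on the other side stand and limit the finding.

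- A reader might infer that any elevation present at entry is reported as on-treatment. It is not: it must be seen again after Day 1.
- ALT above 3 times ULN for more than 4 weeks meets stopping criterion 4 in Protocol 5.8.1, so at that line a carried-over elevation cannot run on indefinitely under treatment. This narrows the case without removing it, because one later value is enough to be counted.
- Exclusion criteria 1 and 4 let the investigator keep out patients with a clinically relevant abnormality or an unstable condition. That is judgement, not a numeric limit, but entry is not unscreened.
- A reader might also infer that the SAP contradicts Protocol 9.3.5.1.3. The documents do not clearly support this. The protocol asks for chemistry to be displayed by grade, and graded listings for 12 patients can arguably meet that. The protocol's own worst-case display carries no baseline condition. What remains is that the SAP's worst-case liver summary appears to be in ULN multiples rather than CTCAE grades, and Section 4 does not say so.
- Adverse event reporting covers part of the gap. Protocol 7.2.2.3 has clinically significant laboratory abnormalities, including worsening from baseline, recorded as events, and SAP 2.1.1 describes on-treatment events as new or worsening. This depends on investigator judgement and gives no tabulated change in liver tests.
- The table shells (SAP Sections 7 to 10) cannot be seen, and the liver lines in the text are examples only. One cannot claim that smaller rises go uncounted, or rule out a baseline column in the shell.

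**Conclusion.** The point holds for the summary tables as described in the visible SAP text: they compare haematology with baseline, do not do so for liver tests, and count a persisting Day 1 elevation together with new ones.

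This is a weakness of presentation and interpretation. No test or estimate depends on it, and the listings let a reader recover each patient's Day 1 value. The 8.3 points per patient is arithmetic on an assumed count. It should not be read as an expected bias, since the documents give no frequency of elevation at entry.

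The change is still worth making, because it is specific, uses data already collected and serves a named safety endpoint. The conclusion assumes that the unseen shells add no baseline comparison.

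**What to change.** 1. In SAP 2.6.3, extend the shift-table bullet so that it covers platelets, hemoglobin, WBC, ALT, AST, ALP and total bilirubin.
2. Define laboratory baseline, which the visible SAP text does not do, as the last value on or before the first dose in this study.
3. State next to the table that this is an on-drug baseline, so the shift describes change during the extension and is not a comparison with an untreated state.
4. Secondary: add one line to SAP Section 4 saying that the worst-case chemistry summary uses ULN multiples rather than CTCAE grade.

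Splitting the liver threshold table by baseline status is optional, because it largely duplicates the shift table.

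The cost is four more parameters in a table already planned, with no new data collection and no change to any clinical rule. The drawback is a few extra tables that will be sparse with 12 patients.
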